6.1 Inclusion Criteria

- 6.1.1 Men and women, 18 years of age or older with cancer.
- 6.1.2 English speakers.
- 6.1.3 CIPN neuropathy: Received neurotoxic chemotherapy in any setting as cancer treatment; including taxanes-such as paclitaxel or docetaxel; platinum-based compounds such as carboplatin or cis-platinum or oxaliplatin; or, vinca alkaloids such as vincristine, vinblastine, or vinorelbine, or proteosome inhibitors such as bortezimib.

NOTE: Patients should no longer be receiving the therapy that caused the CIPN, or have recently started a new treatment that may worsen CIPN. Patients on a treatment that may cause CIPN for a period of time where CIPN does not appear to be worsening may be allowed at discretion at the Principal Investigator.

- 6.1.4 Pain or symptoms of peripheral neuropathy of >3 month's duration attributed to chemotherapy-induced peripheral neuropathy.
- 6.1.5 An average daily pain rating of ≥ 4 out of 10, using the following question from the BPI:

Please rate your pain by circling the one number that best describes your leg and/or feet pain/discomfort (it is understood that the neuropathy discomfort from chemotherapy is not always called a 'pain' by all patients, but, for this study, that 'discomfort' should be considered to be a 'pain') from the chemotherapy related neuropathy on average over the past week. (Scale 0-10; 0= No pain, 10= Pain as bad as you can imagine)

- 6.1.6 Life expectancy >3 months
- 6.1.7 ECOG Performance Status 0, 1, 2, or 3 (see Appendix A).
- 6.1.8 Patient understands the study regimen, its requirements, risks, and discomforts, and is able and willing to sign an informed consent form.

6.2 Exclusion Criteria

- 6.2.1 Any of the following: pregnant women, nursing women, women of childbearing potential or their sexual partners who are unwilling to employ adequate contraception (condoms, diaphragm, birth control pills, injections, intrauterine device [IUD], surgical sterilization, subcutaneous implants, abstinence, etc.).
- 6.2.2 Use of an investigational agent for pain control concurrently or within the past 30 days.
- 6.2.3 History of or previous intolerance to transcutaneous electronic nerve stimulation.
- 6.2.4 Patients with implantable drug delivery systems, e.g. Medtronic Synchromed.
- 6.2.5 Patients with heart stents or metal implants such as pacemakers, automatic defibrillators, cochlear implants, aneurysm clips, vena cava clips and skull plates. (Metal implants for orthopedic repair, e.g. pins, clips, plates, cages, joint replacements are allowed).
- 6.2.6 Patients with a history of myocardial infarction or ischemic heart disease within the past six months.
- 6.2.7 Patients with history of epilepsy, brain damage, or symptomatic brain metastases.
- 6.2.8 Prior celiac plexus block, or other neurolytic pain control treatment.
- 6.2.9 Other identified causes of painful parasthesias existing prior to chemotherapy (e.g., radiation or malignant plexopathy, lumbar or cervical radiculopathy, pre-existing peripheral neuropathy of another etiology: e.g., carpal tunnel syndrome, B12 deficiency, AIDS, monoclonal gammopathy, diabetes, heavy metal poisoning amyloidosis, syphilis, hyperthyroidism or hypothyroidism, inherited neuropathy, etc.) that might be responsible for the patient's current neuropathic symptoms.
- 6.2.10 Skin conditions such as open sores that would prevent proper application of the electrodes.
- 6.2.11 Currently receiving anti-convulsants (such as gabapentinoids, e.g. gabapentin (Neurontin) or pregabalin (Lyrica). Because of data that support that patients do not do as well when on gabapentin or pregabalin, all patients on these medications will be weaned off them prior to study initiation. The study team will provide instructions on how to do this.
- 6.2.12 Other medical or other condition(s) that in the opinion of the investigators might compromise the objectives of the study

6.3 Inclusion of Women and Minorities

Both men and women of all races and ethnic groups are eligible for this trial.

7. Study Design and Treatment Plan

7.1 Summary

We propose a straightforward randomized controlled trial of actual Scrambler Therapy versus sham therapy (electrodes placed on the back, which does not cause pain relief but is perceived as active treatment in a pilot trial). This study also serves to get preliminary information for planning future, larger, phase III studies.

7.2 Recruitment

Patients will be recruited through the Kimmel Cancer Center's outpatient oncology clinics. Participants may also be referred from other centers to consider participation; however, direct recruitment strategies are not planned.

7.3 Determination of Eligibility

Eligibility for participation will be reviewed and confirmed by a member of the study staff. Upon successful eligibility, the patient will be eligible for registration into the study, at which time a study-specific subject ID/number will be assigned.

For patients who reach the study team without the referral of their treating oncologist, a member of the patient's care team will be consulted to confirm that s/he believes that the participant is appropriate for protocol participation.

Study intervention cannot begin until the patient is successfully registered and after randomization has taken place (per below).

7.4 Randomization and Blinding

Upon eligibility confirmation, participants will be randomized to the Scrambler Therapy or sham treatment group. A list will be tabulated by a study statistician and provided to a member of the study team not directly involved in recruitment or provided in a way that the next assignment is not known (i.e., prepared, sealed envelopes to be opened at the time of randomization). The randomization assignments will be made as close as possible the planned day 1 of intervention and made available to the study team member who will administer the Scrambler intervention.

Whenever possible, for any outcome other than a patient-reported outcome, such as diary entries, the data will be recorded or reviewed by the study coordinator, not the treatment person. If possible, the study coordinator will meet with participants prior to or after the treatment session such that the coordinator interacting with the participant is not aware of the treatment assignment.

All participants will be asked whether they thought that they received Scrambler Therapy or sham therapy. This will be evaluated at the end of the first treatment and after the last treatment.

All patients will be un-blinded after the Day 28 data collection is complete. Participants randomized to the sham group who still have an average daily pain rating of ≥ 4 after the day 28 data collection is complete (for the primary endpoint) will be offered 10 Scrambler Therapy sessions. This group will not be separately analyzed or considered part of the primary endpoint;

however, their pain scores recorded after the primary endpoint is assessed will be summarized with the rest of the sham group using an intent-to-treat approach. We will keep to the original 2 and 3 month time periods for assessment, and not add a two week delay, in order to finish at 3 months total. These originally sham-randomized participants with an average daily pain rating of <4 after the day 28 data collection is complete may be offered 10 Scrambler Therapy sessions at the discretion of the Principal Investigator.

7.5 Methods and Intervention

7.5.1 Scrambler Therapy

The locations of symptoms will be assessed on both the upper and lower extremities. Treatment will be given to both arms and legs based on the number of electrodes available and the desire to have a short, defined period of treatment.

7.5.1.1 Treatment Days

Day 1/Treatment Initiation:

1. Treatment should be initiated by turning on the stimulus for the first electrode pair. The intensity of the stimulus is increased until the patient can first feel some sensation associated with one or both of the electrodes.
2. Then, over a few seconds, the intensity is increased to what is maximally tolerated.
3. Once the intensity is at its maximum setting, the research therapist will evaluate the level of pain. If the pain level is not decreased, the machine will be reset to zero, the electrodes will be repositioned and the machine will be restarted in the manner described above. If the pain is not completely resolved with one set of electrodes, a second set will be applied in a similar fashion. Once satisfactory electrode placement and stimulus intensity is determined, therapy is maintained for a total of 30 minutes. The exact assessment and electrode location process is outlined in The Calmare Manual.
4. The same process will be followed for the opposite foot.
5. If a patient develops pain or a burning sensation with any of the electrodes, then the treatment should be interrupted and the electrode should be evaluated. Considerations include subjective patient intolerance, stimulation of a cutaneous nerve branch, or exacerbation of hyperesthesia or allodynia associated with the neuropathic process. These problems can be addressed by moving one or both of the electrodes farther away from the area of pain. For the electrodes that were moved, the intensity should again be increased and maintained at maximum for 30 minutes as described above.
6. Once placement of the electrodes have been finalized, photographs may be taken of the sites of the electrodes including lower arms, hands, lower legs, feet, and lower back to document the placement of the electrodes on each day. These photographs will be documented in the patients' electronic medical record and will not include any identifying features.

Days 2-10:

1. Treatment will be administered using the same principles (each day evaluated independently and not necessarily reproducing the electrode arrangements and

stimulation parameters of the previous day) for 30 minutes on consecutive days (Monday-Friday for 2 weeks).

2. Up to two or three days may be skipped to allow for weekends and/or holidays, if needed. If the participant presents without any pain, then the treatment will be “held” for that day and this information will be recorded.
3. Treatment does not proceed if the patient does not have pain.

7.5.1.2 Dose and Application

1. Electrodes are applied on the skin in the pain-affected area.
2. The electrodes are never applied directly on the pain area, unless there is no pain free area. In that case, the electrode will be applied to the most pain free area, as per the manufacturer’s and inventors instructions.

7.5.2.1 Treatment Days

1. The Sham procedure will be implemented in exactly the same way as the Scrambler Therapy procedure, except that the placement of the electrodes will occur on the back, **not near the spinal column** (away from the main region of pain, which in CIPN is nearly always maximal in the feet).
2. The distal electrode (black) will be placed on the back midway from the posterior axillary line and the midline on the left side in the T8 dermatome.
3. The proximal electrode (non-black) will be placed on the back midway from the posterior axillary line and the midline on the left side in the T4 dermatome.

7.5.2.2 Dose and Application

The electrodes will be applied and sessions will continue similarly as in the Scrambler Therapy group, with the exception of the different placement areas noted.

We will attempt to control for bias by having the lead-placer use the same script and follow exactly the same procedures, asking the exact same questions (“Do you feel any sensation?” “Let me know when you feel the sensation.” “Let me know when you feel the sensation is at your limit of tolerance.”) when placing “real” or sham leads.

7.5.3 Calmare Device

The device has FDA 510(k) approval, "Scrambler ST 5 TENS Device," (K081255) granted in February 2009.

A device has been provided to SKCCC by the manufacturer, Competitive Technologies, Inc. The device has passed approval by Johns Hopkins Clinical Engineering.

7.5.4 Additional Information

We will include information in the informed consent form to suggest that participants wear loose fitting clothing where electrode placement may be easily placed underneath clothing to avoid the need to change into an exam gown at each visit.

7.6 Patient-Reported Outcomes

7.6.1 General

In addition to the patient-reported outcomes described below and as outlined on the Study Calendar, the following information will be collected for all participants:

1. Before and after each Scrambler Therapy/Sham treatment session daily, the “pain now” question from the BPI will be asked and documented, as in prior studies: “Please rate your pain/discomfort on a scale of 1 to 10 with the one number that best tells how much pain/discomfort from the chemotherapy related neuropathy you have RIGHT NOW.”
2. Patients will be asked to state whether they believe they are receiving the active or sham therapy at the end of the 1st and last treatment.
3. Patients will be asked after the end of the last treatment: “Did the treatment help you with the pain and or numbness?” Yes/ No. “Would you want to continue the treatment if it was available?” Yes/No

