5.3.2 Preliminary data on Scrambler therapy

The Scrambler Therapy device appears to work on pain based on results from multiple trials. In the first trial, 11 cancer patients (3 pancreas, 4 colon, 4 gastric) suffering from drug resistant visceral pain were studied during their first ten treatment sessions.³¹ Pain was quickly and markedly reduced and maintained until death. Nine of 11 stopped pain drugs within the first 5 applications. In the second trial, 226 patients with neuropathic pain including failed back surgery, brachial plexus neuropathy, and others were treated.³² 80% of patients responded with > 50% pain relief, 10% responded with pain relief from 25% to 49%, and only 10% had no response (P<0.0001).

Based on these results the FDA approved Scrambler therapy for cancer pain treatment February 25, 2009. In clinical practice, over 4000 patients have been treated worldwide with no reported side effects except occasional transient worsening of pain. In addition, at least one patient had some temporary bruising under the sites of the electrodes.

In the first US trial, Smith et al³³ studied 16 typical patients (median age 56, usual chemotherapy drugs) with refractory CIPN and pain scores over 6. Each patient was treated for 10 sessions of 60 minutes each, Monday through Friday. The electrodes were applied in the areas of the pain, as shown in Figure 2. The results are shown in Figure 3. *The average pain reduction was 59%, similar to direct spinal cord stimulation.* The effect on some patients was dramatic, with 4 people having no pain and several resumed normal activity. The effect was persistent, lasting weeks to months in most patients, with successful retreatment if needed.

Mayo Clinic investigators have now replicated these results in a pilot trial, with a 47% reduction in CIPN pain.³⁴ The 10 day time period is too short for any

Figure 2:MC5-A Scrambler Therapy for CIPN, application of electrodes for

[figure not shown]

Figure 3: Scrambler Therapy and CIPN Results, Smith et al.

[figure not shown]
[figure not shown]

Figure 5: Scrambler Therapy and Neuropathic Pain, Ricci et al.

natural reduction in CIPN, making this unlikely to be natural resolution. (Figure 4)

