7.6.2 BPI Short Form – Modified for CIPN

The Brief Pain Inventory (BPI) short form⁴⁴ is a pain assessment tool used with cancer patients to measure both severity of pain (first 5 items) and interference caused by pain (item 6 with 7 components) on 0-10 scales (0=does not interfere; 10=completely interferes.) It is widely used in cancer pain evaluation⁴⁵ and has been modified specifically for neuropathy⁴⁶.

The BPI short form will be completed at baseline, end of treatment and at 1 month (28 days), 2 months (8 weeks), and 3 months (12 weeks) after the Scrambler/Sham therapy. Those participating in sham therapy group and choosing Scrambler therapy after 28 days, will complete the BPI at the end of Scrambler therapy, and at 1 and 2 months after the Scrambler therapy. Before and after Scrambler/Sham therapy daily, the “pain now” question from the BPI (question #4) will be asked and documented, as in prior studies.

7.6.3 European Organization for Research and Treatment of Cancer Quality of Life Cancer Chemotherapy Induced Peripheral Neuropathy-20 Instrument (CIPN-20)

The EORTC QLQ-CIPN20⁴⁷ is a 20-item CIPN-specific questionnaire which includes three scales assessing sensory (9 items: #31-36, 39, 40, 48), motor (8 items: #37, 38, 41-45, 49), and autonomic (3 items: #46, 47, 50) symptoms and functioning with each item measured on a 1-4 scale (1 – not at all; 4 – very much). The EORTC QLQ-CIPN20 has been tested in cancer patients receiving a variety of chemotherapies and has been shown to have internal consistency reliability based on Cronbach’s alpha coefficients of 0.82, 0.73, and 0.76 for the three scales, respectively, with excellent validity and reliability⁴⁸. The CIPN-20 will be completed at baseline, end of treatment and at 1 month (28 days), 2 months (8 weeks), and 3 months (12 weeks) after the Scrambler/Sham therapy. Those participating in sham therapy group and choosing Scrambler

therapy after 28 days, will complete the CIPN-20 at the end of Scrambler therapy, and at 1 and 2 months after the Scrambler therapy.

NOTE: Please see questionnaires in Appendices A and B.

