13.1 Overall

The primary endpoint is change in patient-reported pain from day 0 to day 28 as measured by the Modified Brief Pain Index, question #3 (Appendix B). This endpoint also serves to get preliminary information for planning future, larger, phase III studies.

Secondary endpoints will include the total Brief Pain Inventory score, the sensory and motor subscales of the CIPN 20, and the Morphine Oral Equivalents Dose at day 28 compared to sham therapy. We will also report the daily (days 1-10) changes in “pain now” before and after each treatment, to be comparable to all the other reported studies.

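### The scripted daily pain-now question runs from 1 to 10 against a 0-10 instrument, so a pain-free post-session reading has no value; the effect is small and confined to the daily series

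*Combined protocol and SAP*

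**What the plan says.** Section 7.6.1 requires the BPI pain-now question before and after each Scrambler or sham session and gives its wording: "Please rate your pain/discomfort on a scale of 1 to 10". Section 7.6.2 states that each day the pain-now "question from the BPI (question #4) will be asked and documented, as in prior studies", and describes the BPI short form as a tool "to measure both severity of pain (first 5 items) and interference caused by pain (item 6 with 7 components) on 0-10 scales".

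Appendix B prints question 4 as a circle-one-number item with no mention of 1 to 10. Its response lines for questions 1 and 3 run from 0 to 10 with no pain at 0. A note there commits the study to the printed wording for all questions, even if the layout changes. The response line for question 4 itself is not visible in the text available for review, so nothing here rests on it.

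Section 13.1 says the daily changes will be reported "to be comparable to all the other reported studies". Section 7.5.1.1 deals with pain-free arrivals: "If the participant presents without any pain, then the treatment will be" held that day, and the fact is recorded. The primary endpoint is a different item, question 3, on 0-10 (Sections 1 and 13.1).

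**The concern.** A scale that starts at 1 has no number for a patient whose pain has gone. The protocol expects that state to occur: it holds sessions for patients who arrive without pain, and on Day 1 it adds electrodes while pain is not fully resolved. The reading straight after a session is where a zero is most likely.

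If the script is followed, a true zero is entered as 1 or improvised by the person asking. Relief is then slightly understated, more so in whichever arm has more pain-free readings. If Scrambler works, that is the active arm, and the daily contrast moves toward no difference.

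The same item is also answered on the BPI form before the first session on Day 1 (Study Calendar). A patient could therefore meet it twice that day, once on 0-10 and once on 1-10, and the data would not show which scale a 1 came from.

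**Working it through.** The plan states no figure for this point, so the check is a comparison of texts followed by an estimate of the consequence.

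**1. The texts.** Section 7.6.1 says 1 to 10. Section 7.6.2 says BPI question 4, on an instrument with 0-10 scales. Appendix B prints question 4 without 1 to 10 and promises the printed wording. These cannot all be followed. The documents do not say which version is read to patients.

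**2. Largest recordable reduction.** With a floor of 1 and a starting score b, the largest proportional fall is (b - 1)/b. Section 13.2 expects b between 4 and 6.

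- b = 4: 3/4 = 75%
- b = 5: 4/5 = 80%
- b = 6: 5/6 = 83%

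On 0-10 the limit is 100% in each case. For comparison, the earlier randomized pilot in Section 5.3.2 reports a fall from 8.1 to 0.7, which is 1 - 0.7/8.1 = 91%. With a floor of 1 the limit from 8.1 would be 7.1/8.1 = 88%, and a mean of 0.7 could not arise.

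**3. Effect on the arm difference.** Each true zero is raised by 1 point and no other reading changes. The loss in the between-arm difference, in points, is therefore P(true zero, Scrambler) - P(true zero, sham).

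*(a) The plan's own model.* Inputs from Section 13.2: bivariate normal scores; baseline mean 4, SD 2; post-treatment mean 2 (Scrambler) or 3.6 (sham), SD 1.5; correlation 0.3; patients outside the stated limits replaced; scores then rounded. As a check on the implementation, this gave power of 84-85%, 88% and 75-76% against the plan's 87.3%, 86.6% and 77.6%. The first is 2.5 to 3 points low, slightly more than the 2.2-point simulation error of 1000 runs. That is close enough for an order of magnitude.

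| | Scrambler | Sham | Difference |
|---|---|---|---|
| True zeros after treatment | 5.10% | 0.55% | 4.55 percentage points |
| Mean fall, 0-10 | 3.07 | 1.60 | 1.47 |
| Mean fall, floor of 1 | 3.02 | 1.59 | 1.43 |

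Loss: 0.0510 - 0.0055 = 0.0455, about 0.05 points. Relative to the difference on 0-10, 0.0455/1.47 = 3%. The model replaces negative draws instead of setting them to zero, which keeps zeros rare.

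*(b) A larger illustration.* The first US trial treated 16 patients, "with 4 people having no pain" (Section 5.3.2). Assuming 4/16 = 25% zeros under Scrambler and none under sham, the loss is 0.25 x 1 - 0 x 1 = 0.25 points.

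**The case against.** The strongest reply is that this is a slip in one sentence and that little depends on it. Most of that stands.

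- **Complete relief is recorded elsewhere.** The full BPI, on 0-10 scales, is completed at end of treatment and at 1, 2 and 3 months, and its relief item runs to 100%. A reader might infer that the trial cannot record complete relief at all. The documents do not support that; only the readings around sessions are affected.
- **Pain-free arrivals have their own record.** The held session is documented, so the gap is narrower: the plan does not say what pain score, if any, is entered for that day.
- **Comparability is not lost.** Readings of 1 or more are unchanged. Section 7.6.1 introduces its wording as that of prior studies, and the documents give neither the wording nor the scale of those studies' daily item. The 0.7 mean and the pain-free patients suggest that zero was available, but the item used is not stated.
- **The 0.25 figure transfers poorly.** It comes from a single-arm pilot with 60-minute sessions and pain scores over 6, with neither item nor timing given. This trial uses 30-minute sessions and expects 4-6.
- **The outcome is descriptive.** Section 13.1 only reports the daily changes, and 13.3.2 makes all secondary p values descriptive.

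None of this removes the contradiction. A verbatim script for data collection conflicts with the instrument it claims to use, on the most frequently collected outcome.

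**Conclusion.** The contradiction between 7.6.1 and both 7.6.2 and Appendix B is certain on the text. If the script is read as written, a pain-free post-session reading has no value. Relief in the daily series is then understated by at most 1 point per reading, and only where true pain is zero.

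The expected loss in the arm difference is about 0.05 points (3%), assuming that the sample-size model describes readings on days 1-10, which the plan does not claim. About 0.25 points is an upper illustration and should not be read as the expected bias. The direction is toward no difference only if Scrambler produces more zeros than sham.

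The stated aim of comparability is impaired at the bottom of the scale and nowhere else. The primary endpoint, sample size and scheduled BPI assessments are untouched. Severity is minor.

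**What to change.** Replace the question in 7.6.1 with the Appendix B question 4 wording on a 0-10 scale, with 0 labelled as no pain. State what pain score is entered when a session is held because the patient has no pain.

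Section 9 reports that 14 patients have already been treated on this study. For them, record which scale was read. If it was 1-10, report the daily series accordingly, for example with a sensitivity summary that treats a 1 given under that script first as 1 and then as 0.

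The cost is a one-line text change, made as an amendment under 12.1, and a small check of existing records. If 1-10 was in use, the correction leaves two scales in the daily series, which is why the scale must be flagged for each patient. If the Appendix B wording was in use throughout, only the protocol text changes.
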